## 5.4 Objectives

### Primary Objectives

1. To evaluate the antibody response to dengue virus following administration of the second dose of QdengaTM via the intradermal route.
2. To evaluate the T-cell response (CD4 and CD8) to dengue virus following administration of the second dose of QdengaTM via the intradermal route.

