## 5.5 Literature review

Dengue fever, attributable to the dengue virus, represents a substantial global health concern. The advent of vaccines such as Qdenga and Dengvaxia has demonstrated potential in conferring immunity

against all four serotypes of the dengue virus. However, given the higher prevalence of dengue fever in resource-limited tropical regions, it is crucial to explore cost-reduction strategies. Intradermal injection, a previously successful dose-sparing technique, offers one such strategy. Nonetheless, the efficacy of intradermal administration for the newly developed Qdenga vaccine remains uncertain and warrants further investigation.

Study on the immunogenicity of the Qdenga vaccine, given subcutaneously, have shown promising results. One randomized, placebo-controlled Phase 2 study involving 148 participants aged 1.5 to 45 revealed seropositivity rates at month 36 of 97.3%, 98.7%, 88.0%, and 56.0% for DENV-1, -2, -3, and -4, respectively. Notably, seropositivity for DENV-4 varied significantly based on initial serostatus, with 89.5% in seropositive individuals compared to 21.6% in seronegative individuals. No vaccine-related serious adverse events (SAEs) were reported. The study demonstrated the persistence of neutralizing antibody titers and the Qdenga vaccine's tolerability over three years in both children and adults living in dengue-endemic regions.

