Another study evaluated the safety and immunogenicity of an early low-dose tetravalent dengue vaccine candidate (LD-TDV), which uses an attenuated serotype 2 backbone, administered intradermally either with an injector device (PharmaJet) or a needle-syringe in 67 subjects. The findings indicated that the intradermal administration of LD-TDV was well tolerated, with no significant safety concerns, and induced an immune response against all four dengue serotypes. The overall tetravalent seroconversion rates were 13.8% at Day 28 and 31.0% at Day 118, comparable to the previously reported 25% seroconversion rate for low-dose TDV given intradermally in 72 flavivirus-naive adults. Local reactions, such as induration (91.7% vs. 12.5%;  $P < .0001$ ) and pruritus (50% vs. 8.3%;  $P = .0034$ ), were more frequent following intradermal vaccination compared to subcutaneous administration. Most of these reactions were mild and resolved within one day.

This study aims to ensure the safety of vaccine recipients by comparing the administration of a second dose via the intradermal (ID) route after an initial subcutaneous (SC) dose with a control group receiving both doses subcutaneously (SC-SC). Previous research in Thailand on COVID-19 vaccines also evaluated the safety and immunogenicity of fractional (1/5th or 1/6th) doses of homologous ChAdOx1 or BNT162b2 administered intradermally following an initial intramuscular (IM) dose, demonstrating safety and immunogenicity. Based on this, the study hypothesizes that intradermal administration of fractional doses of the Qdenga vaccine after an initial SC dose will be immunogenic and have acceptable systemic adverse effects, with potential utility as a booster in the future.

The potential of intradermal vaccination to maintain or enhance immunogenicity while reducing the required dose has been highlighted in several reviews. This method could lower costs and improve vaccine accessibility in low-resource settings. However, further research is needed, as no randomized studies have yet evaluated both humoral and cell-mediated immune responses to intradermal Qdenga vaccination.

[figure not shown]

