### 5.7.3 Study samples

#### 5.7.3.1 Inclusion Criteria

1. Thai adult aged 18-60 years with positive dengue IgG from screening test, who not previously received dengue vaccine.
2. The subjects are able to and willing to comply with the requirements of the clinical trial program and could complete the 3-month follow-up of the study.
3. Individuals who are in good health condition at the time of entry into the trial as determined by medical history, physical examination and clinical judgment of the investigator and meet the requirements of immunization
4. The subject can provide with informed consent and sign informed consent form

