#### **5.7.6 Sample size calculation**

In this study, a total sample size of 24 participants will be used, allocated equally into two groups of 12 participants each. Based on the recommendation by Julious, a sample size of 12 subjects per group is considered adequate to achieve reasonable precision for preliminary estimates in a pilot study.

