### 5.7.8 Study variables and their definition

Independent variables

- Technique of vaccination: subcutaneous vs. intradermal
- Sex
- Age

Dependent variables

- ELISA: Antibody level for dengue at day 0, 30, 120
- ELISpot: T cell responses against dengue antigens at day 0, 30, 120
- Adverse event following vaccine (AEFI)

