### Arms and Interventions:

Arm 1: subcutaneous Qdenga for 1st vaccination then intradermal Qdenga for 2nd vaccination

Arm 2: subcutaneous Qdenga for 1st vaccination then subcutaneous Qdenga for 2nd vaccination

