#### **Data analysis**

(1) Record and analyze data: using the R program version 3.5.1

(2) Analysis data:

- Continuous variables using Mean  $\pm$  SD or Median (IQR)
- Discrete variables using percentage
- Compare qualitative variables data using Pearson's Chi-squared test or Fisher's exact test
- Compare quantitative variables data using Student's t-test or Wilcoxon rank-sum test
- A probability value (P) <0.05 was considered significant

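### The unadjusted Day 120 comparison of the two second-dose routes is valid, but adjusting it for one pre-dose-2 value would narrow the interval on average if the correlation exceeds about 0.23.

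*Combined protocol and SAP*

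**What the plan says.** The Data analysis part of section 5.7.12 gives one line for comparing quantitative outcomes: "Compare quantitative variables data using Student's t-test or Wilcoxon rank-sum test". It names no contrast, time point, covariate, change score or model, and it plans P values but no confidence interval.

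The contrast has to be inferred. The first primary objective in section 5.4 is "To evaluate the antibody response to dengue virus following administration of the second dose of Qdenga" by the intradermal route. Section 5.5 describes a comparison of that regimen with an SC-SC control group. Section 5.6 has the second-dose route randomised, and Arms and Interventions gives both arms the same subcutaneous first dose. The implied comparison is therefore SC-ID against SC-SC, 30 days after dose 2 (Day 120).

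Earlier values of the same outcomes are already planned. Section 5.7.8 lists "ELISpot: T cell responses against dengue antigens at day 0, 30, 120", and lists the ELISA antibody level on the same days.

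The sample size of 12 per group is justified in section 5.7.6 by precision: "a sample size of 12 subjects per group is considered adequate to achieve reasonable precision for preliminary estimates in a pilot study".

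**The concern.** The plan collects a participant's own earlier antibody and T-cell values but does not say that the comparison of arms will use them. If people who start high tend to finish high, part of the Day 120 spread is predictable, and an unadjusted test treats that part as noise. This pilot rests its size on precision and has only 24 participants, so a between-arm interval that is wider than necessary is a real, if modest, loss.

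A value taken before dose 2 is a legitimate covariate. Both arms have had the same treatment up to then, so the route of dose 2 cannot have affected it. This is so whether randomisation takes place at Day 0 (Study procedure table) or after the first dose (section 5.6).

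What is at stake is efficiency. Bias and validity are not in question.

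**Working it through.** **Inputs from the plan.** 12 per arm, 24 in total (section 5.7.6; 2 × 12 = 24). Significance level 0.05 (Data analysis), taken as two-sided. The size comes from a pilot recommendation, so there is no power, SD or interval width to reproduce.

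**Inputs assumed.** The correlation r between the pre-dose-2 value and the Day 120 value is not in the documents; a range of 0 to 0.8 is shown. Readouts are taken as approximately normal on the analysis scale. Widths are in units of the within-arm SD.

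**Unadjusted 95% half-width.** t(0.975, 22) × √(2/12) = 2.0739 × 0.4082 = 0.847 SD.

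**ANCOVA 95% half-width.** t(0.975, 21) × √(2/12) × √[(1 − r²)(1 + 1/20)], with t(0.975, 21) = 2.0796. The factor 1 + 1/20 is the expected cost of chance covariate imbalance, 1 + 1/(2n − 4) with n = 12.

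| r | ANCOVA half-width (SD) | Change against 0.847 |
|---|---|---|
| 0 | 0.870 | 2.8% wider |
| 0.2 | 0.852 | 0.7% wider |
| 0.3 | 0.830 | 2.0% narrower |
| 0.5 | 0.753 | 11.0% narrower |
| 0.7 | 0.621 | 26.6% narrower |
| 0.8 | 0.522 | 38.3% narrower |

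**Equivalent size.** The unadjusted number per arm m that gives the same width solves t(0.975, 2m − 2) × √(2/m) = ANCOVA half-width. For r = 0.3 / 0.5 / 0.7 it is 12.4 / 14.8 / 21.2. At r = 0.3 the gain is less than half a participant per arm.

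**Break-even.** Setting the two half-widths equal gives r = √[1 − (2.0739/2.0796)²/1.05] = 0.230. With fewer analysed it rises to 0.243, 0.258 and 0.277 at 11, 10 and 9 per arm. The plan states no dropout allowance, so these sizes are an assumed range.

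**Simulation check (normal data, 200,000 trials per r).** The ratio of mean widths is 1.001 at r = 0.22, 0.999 at 0.23 and 0.996 at 0.24, which agrees with the formula. The threshold concerns the average. ANCOVA gave the narrower interval in about 41% of single trials at r = 0.23, 53% at 0.3, 85% at 0.5 and 99% at 0.7.

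**Scale check.** A skewed readout was simulated as exp(1.151z), with z normal, 12 per arm and an assumed shift of 1 SD on the log scale. Power at r = 0.3 / 0.5 / 0.7:
- ANCOVA on the raw scale: about 40 / 45 / 57%
- unadjusted rank-sum test: about 60% throughout
- ANCOVA on the log scale: 67 / 75 / 89%

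Adjustment on an unsuitable scale therefore does worse than a test already in the plan; on a suitable scale it does better.

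**What the documents say about r.** Section 5.5 reports, at month 36 of an earlier study, that "seropositivity for DENV-4 varied significantly based on initial serostatus, with 89.5% in seropositive individuals compared to 21.6% in seronegative individuals". This supports a positive direction for antibody. The present trial, however, enrols only a "Thai adult aged 18-60 years with positive dengue IgG from screening test", which removes the seronegative group and may weaken the correlation. Nothing in the documents bears on the correlation for ELISpot.

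**Which earlier value exists.** Sections 5.6 and 5.7.8 give Day 0, Day 30 and Day 120. Section 5.7.9 has blood taken before the booster and 30 days after. The Study procedure table, as extracted, marks blood at Day 0, at dose 2 (Day 90) and at Day 120, with none at Day 30; its asterisk footnote is not in the text available. Day 0 is common to sections 5.6 and 5.7.8 and to the table.

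**The case against.** The strongest case against has four parts.

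- **The gain is conditional.** The correlation is unknown, the cited serostatus contrast is for one serotype at month 36, and enrolment removes that contrast by design. At r = 0.3 the gain is trivial, and in a trial run once the interval may come out wider. All of this stands, and it is why the claim is limited to average width and shown over a range.
- **The rank-sum option.** The half-widths are set against the t-test, while the plan also allows a rank-sum test. The scale check bears this out: ANCOVA should not replace the rank-sum test for a markedly skewed readout left untransformed. Values at a floor or ceiling, or a responder count (section 5.7.9 speaks of a number of T-cell responders), raise the same difficulty.
- **The plan might already use earlier values.** A t-test on change would fit its wording. That is possible, but it is not stated. With equal variances at the two times, the simulated change-score interval is 18% wider than the unadjusted one at r = 0.3, about equal at 0.5 and 23% narrower at 0.7. ANCOVA is narrower on average at each of these.
- **The between-arm interval may not be the deliverable.** Section 5.7.6 speaks only of preliminary estimates, which could be per-arm summaries, and no confidence interval is planned. This stands, and it limits the importance of the point.

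A reader might infer that the planned tests are biased or invalid. The documents do not support that: with a randomised second-dose route, the unadjusted comparison is valid. A reader might also expect a gain of a quarter or more. That needs a correlation near 0.7, for which the documents give no evidence.

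**Conclusion.** The point holds as an efficiency improvement. The plan lists only unadjusted tests and does not call for pre-dose-2 values that it already intends to measure. With 12 per arm and an approximately normal scale, ANCOVA on one such value is narrower on average above r of about 0.23 (0.28 with 9 per arm). The trade-off is uneven: at worst about 3% wider at zero correlation, against 11% to 27% narrower at 0.5 to 0.7.

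This rests on an assumed correlation, on a suitable analysis scale, and on the inference that SC-ID against SC-SC at Day 120 is the intended contrast. The case is weaker for ELISpot than for antibody, because the documents say nothing about its correlation over time.

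**What to change.** In the Data analysis section:

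1. For continuous readouts on a suitable scale (log where the readout allows it), make the between-arm Day 120 analysis an ANCOVA on arm plus the same readout at one pre-specified time before dose 2, the same time for every participant.
2. Name that time. Day 0 needs no extra assay. A later pre-dose-2 time can be used instead once sections 5.6 and 5.7.8 are reconciled with section 5.7.9 and the Study procedure table.
3. Report the adjusted difference, or the ratio on a log scale, with a 95% confidence interval.
4. State a rule for a missing covariate value; otherwise that participant drops out of the model.
5. Keep the rank-sum or categorical test as the main analysis where a readout is markedly skewed, sits at a floor or ceiling, or is a responder count, and cannot be put on a suitable scale. Elsewhere keep the rank-sum test as a sensitivity analysis.

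**Cost.** A few lines of text, one regression in R, one degree of freedom (21 instead of 22), and an interval about 3% wider on average if the correlation is near zero. Choosing the sample taken just before dose 2 would add up to 24 ELISA and ELISpot runs (one per participant for each assay); choosing Day 0 adds none.

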## 5.3 Rationale

As in the setting of low- to middle-income countries, to demonstrating that lower doses of vaccine via intradermal route can still elicit robust immune responses, thereby lowering the overall cost of vaccination might be particularly meaningful ,with possible extra benefit of experiencing fewer side effects or risk of allergy. This study goal is to explores the potential of intradermal administration of Qdenga, hypothesizing that a lower dose via this route could achieve adequate immunogenicity compared to the standard subcutaneous administration, thus offering a cost-effective alternative particularly in low-resource settings where dengue is most prevalent.

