## 5.6 Conceptual framework

A new dengue vaccine, Qdenga™, has recently become available in Thailand. As a live-attenuated vaccine, it does not require pre-vaccination serological screening for dengue immunity, unlike Dengvaxia™. However, access to Qdenga™ remains limited due to its high cost and the fact that it is not yet reimbursable for the general population. The vaccine is designed for subcutaneous administration and is given as a two-dose series, with the second dose administered three months after the first.

In theory, intradermal administration may elicit comparable immune responses while using a lower vaccine dose, owing to the high density of antigen-presenting cells in the dermal layer. Based on this rationale, investigators from multiple departments within the Faculty of Medicine have initiated a collaborative study to evaluate the immunogenicity and safety of intradermal Qdenga™ administration in healthy volunteers. Immune responses will be assessed at baseline, 30 days after the first dose, and 30 days after the second dose. All participants will receive the first dose subcutaneously as per standard practice, then be randomized to receive the second dose either subcutaneously or intradermally.

This study aims to enhance understanding of the immune response elicited by Qdenga™ given via different administration routes and to generate data that may inform future vaccine implementation strategies and potential dose-sparing approaches.

CONSORT FLOW Diagram

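### The hypothesis is adequacy compared with subcutaneous dosing, but the plan only tests for a difference at P<0.05 and reports no between-arm estimate with a confidence interval

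*Combined protocol and SAP*

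**What the plan says.** Three parts of the combined protocol and SAP bear on this point.

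- **Hypothesis.** Section 5.3 (Rationale) hypothesises that "a lower dose via this route could achieve adequate immunogenicity compared to the standard subcutaneous administration". Section 5.5 names a control group given both doses subcutaneously and expects that the fractional intradermal second dose "will be immunogenic and have acceptable systemic adverse effects, with potential utility as a booster in the future". Section 5.6 adds, as theory, that "intradermal administration may elicit comparable immune responses while using a lower vaccine dose".
- **Size.** Section 5.7.6 sets 24 participants, 12 per arm, because "a sample size of 12 subjects per group is considered adequate to achieve reasonable precision for preliminary estimates in a pilot study". It gives no effect size, SD, power or margin.
- **Analysis.** The data analysis part of 5.7.12 lists mean and SD or median and IQR, percentages, chi-squared or Fisher tests for categorical data, and for continuous data "Compare quantitative variables data using Student's t-test or Wilcoxon rank-sum test". Its one inferential criterion is "A probability value (P) <0.05 was considered significant".

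No confidence interval, between-arm difference or ratio, margin, response threshold or other definition of adequate appears. The two primary objectives in 5.4 are worded as evaluations of the antibody and T-cell responses after the second dose. Section 5.7.8 measures both at days 0, 30 and 120.

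**The concern.** Adequate compared with the standard route means not much worse than the standard route. A test of no difference can count against that claim when P is small. It cannot support the claim when P is large, because a large P is also what a small or noisy trial produces when a real loss of response is present.

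The size was justified by the precision of estimates, so one would expect the analysis to report an estimate with its precision. It plans a P value instead. If the trial ends with P>0.05, the report will have no planned quantity showing how large a loss the data still allow, and a reader could take non-significance as support for the lower dose. Section 5.6 says that the data may inform dose-sparing approaches, so that misreading would matter.

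**Working it through.** **Inputs from the documents.** 12 per arm (5.7.6). Significance level 0.05, and t-test or Wilcoxon (5.7.12). Sidedness is not stated; two-sided is assumed.

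**Inputs assumed.** The documents give no SD and no analysis scale. I take a between-person SD of 0.3 to 0.6 on the log10 scale, and a true halving of the response as the illustrative loss (log10 2 = 0.301).

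**Step 1. The plan's own figure.** 2 × 12 = 24 is consistent. With no effect size, SD, power or margin, there is no sample-size formula to reproduce.

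**Step 2. Precision, free of any assumed SD.** The 95% interval half-width for a difference in means is t(0.975, 2n−2) × √(2/n), in units of the pooled SD.

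- n = 12: 2.074 × √(2/12) = 2.074 × 0.408 = 0.847 SD
- n = 10: 2.101 × √(2/10) = 2.101 × 0.447 = 0.940 SD

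The t-test has 80% power for a true difference of 1.20 SD and 50% power for 0.837 SD.

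**Step 3. What this means for a halving, by assumed SD.** The noncentrality is 0.301 / (SD × 0.408), and power comes from the noncentral t with 22 df. The lowest observed ratio that is still non-significant is 10^(−0.847 × SD), with SD taken as the observed pooled value.

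| log10 SD (assumed) | Noncentrality | Power, t-test | Halving non-significant | Lowest non-significant observed ratio | Power, Wilcoxon (simulated) | Power, t-test, 10 per arm |
|---|---|---|---|---|---|---|
| 0.3 | 2.46 | 65% | 35% | 0.56 | 60% | 57% |
| 0.4 | 1.84 | 42% | 58% | 0.46 | 38% | 36% |
| 0.5 | 1.47 | 29% | 71% | 0.38 | 27% | 25% |
| 0.6 | 1.23 | 22% | 78% | 0.31 | 20% | 19% |

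**Step 4. Where a halving becomes more likely missed than found.** Power is 50% when 0.301 / SD = 0.837, so SD = 0.301 / 0.837 = 0.36 (12 per arm, t-test). Below that SD a halving is more often detected: power is 81% at 0.25 and 94% at 0.2.

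**Step 5. Could 12 per arm carry a formal non-inferiority claim?** Take an illustrative 2-fold margin, a true ratio of 1, one-sided 0.025 and 80% power. Then n per arm = 2 × (1.960 + 0.842)² × SD² / 0.301², which gives 16, 28, 44 and 63 at SD 0.3, 0.4, 0.5 and 0.6. At SD 0.25 it gives 11, so 12 per arm is enough only at about 0.25 or below.

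**The case against.** The strongest reply is that this is a declared pilot. Its objectives are to evaluate responses, its size is for preliminary estimates, and no sentence says that P>0.05 means adequate. That is correct. A reader might infer from the single P<0.05 criterion that non-significance is the planned route to success. The documents do not say so, and this is a risk of misreading rather than a stated rule. The pilot label does not remove the gap, however: a study sized for estimation should report an estimate with its interval.

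Other parts of the reply also stand.

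- The comparable response in 5.6 is introduced as theory. Only 5.3 states a comparative hypothesis, and the version in 5.5 is about being immunogenic, which is not a between-arm claim.
- Where means and SDs are reported with 12 per arm, a reader could compute the interval. So precision is not wholly hidden; what is missing is a planned between-arm interval.
- The log scale is assumed here. Section 5.7.8 names an antibody level by ELISA without a scale. The ELISpot method subtracts negative-control values, so zero or negative results can occur and a geometric ratio may be undefined.
- The documents offer no basis for a margin, and step 5 shows that 12 per arm would rarely meet one. A compulsory non-inferiority rule would be out of proportion in 24 people.

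**Conclusion.** The concern holds as a mismatch. The hypothesis is adequacy compared with subcutaneous and the size rests on precision, but the planned analysis is a test for a difference with no between-arm estimate and interval. That analysis cannot support the hypothesis, and the text does not guard against reading non-significance as support.

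The 0.85 SD half-width (0.94 SD with 10 evaluable per arm) needs no assumed SD. The chance that a halving goes undetected does: 35% to 78% for an assumed log10 SD of 0.3 to 0.6. It is tempting to say that a halving would usually be missed. The documents do not support that, because it is true only if the SD exceeds about 0.36 and they give no SD.

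This should be fixed, but it does not invalidate the pilot or call for a larger one.

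**What to change.** In 5.7.12:

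- Make the main result for each primary objective the Day 120 intradermal-versus-subcutaneous effect with a two-sided 95% confidence interval. For antibody, use a geometric mean ratio if the analysis is on the log scale. For background-subtracted ELISpot counts, use a difference in means or a Hodges-Lehmann shift.
- State that P>0.05 will not be read as adequate or comparable, and that the result is a preliminary estimate for sizing a later trial.
- Optionally, if the investigators wish to claim adequacy, fix the margin before laboratory and participant data are linked, which 5.7.10 places at the final stage of the study.

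In 5.7.6, state the precision that 12 per arm delivers: a 95% half-width of 0.85 SD for the between-arm difference.

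This changes wording in two sections and needs no extra participants, visits or assays. The price is a less favourable conclusion when the interval is wide. Adopting the optional margin would cost more, because it needs a justification that the documents do not now contain.

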##### Antibody analysis

- Detection of dengue-specific human Abs by ELISA
- Mixtures of all four DENV serotypes were captured onto a MAXISORP immunoplate (NUNC) coated with mouse anti-E antibody (4G2) or anti-NS1 antibody (NS1-F3). DENV captured wells were then incubated with B cell line (BCL) culture supernatants followed

by alkaline phosphatase (AP)-conjugated anti-human IgG Abs. The reaction was visualized by the addition of PNPP substrate. The reaction was stopped with NaOH.

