#### **Peptides**

[figure not shown]
- 15-mer peptides overlapping by 5 amino acids corresponding to sequences of dengue serotype 2 strain 16681 (CprM, E, NS1, NS2, NS3, NS4, and NS5) and to the NS3 sequences of dengue serotype 1 strain Hawaii, dengue serotype 3 strain H87, and dengue serotype 4 strain H241 were synthesized to >80% purity (Sigma Aldrich). Lyophilized peptides were resuspended in dimethyl sulfoxide (DMSO; Sigma) at 80 mg/mL for peptide mixtures. The overlapping peptides were grouped together in pools corresponding to individual dengue proteins (dengue 2: CprM-26, E-97, NS1-71, NS2-70, NS3-123, NS4-70, NS5-95, dengue 1 NS3-124, dengue 3 NS3-124, and dengue 4 NS3-124). The final concentration of any single peptide was 2  $\mu$ g/mL, and the final concentration of DMSO was <1% in all experiments.

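### No antibody or T-cell readout is named as primary; if all 12 described were tested at Day 120 at P<0.05, the chance of a false route difference could reach about 46%

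*Combined protocol and SAP*

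**What the plan says.** Section 5.4 gives two primary objectives: "To evaluate the antibody response to dengue virus following administration of the second dose" and "To evaluate the T-cell response (CD4 and CD8) to dengue virus following administration of the second dose", in both cases by the intradermal route. Section 5.7.8 turns these into one general ELISA antibody level and one general ELISpot variable, "T cell responses against dengue antigens at day 0, 30, 120".

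The detail is in the laboratory methods of section 5.7.9. Under Antibody analysis, the ELISA plates are "coated with mouse anti-E antibody (4G2) or anti-NS1 antibody (NS1-F3", so two capture formats are described, joined by the word *or*. Under Peptides, "The overlapping peptides were grouped together in pools corresponding to individual dengue proteins". The pools listed are "dengue 2: CprM-26, E-97, NS1-71, NS2-70, NS3-123, NS4-70, NS5-95, dengue 1 NS3-124, dengue 3 NS3-124, and dengue 4 NS3-124": seven for dengue 2 and one NS3 pool for each of the other three serotypes. No total or other combined T-cell response is defined.

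For between-arm comparison of continuous outcomes, section 5.7.12 says "Compare quantitative variables data using Student's t-test or Wilcoxon rank-sum test", followed by "A probability value (P) <0.05 was considered significant". It names no primary readout, no visit and no approach to multiple tests, and no other section does so.

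**The concern.** The objectives name two kinds of response, but the methods can produce a dozen numbers per participant at a visit. The plan does not say which number carries the conclusion. Any readout that falls below 0.05 can be labelled significant under the plan's own rule, and a reader of the report could not tell whether it was chosen in advance.

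Section 5.6 says the results may inform later implementation and dose-sparing work, so a chance finding in one pool has somewhere to go. With 12 per arm it would also look large. A two-sided t-test reaches P<0.05 only when the observed difference exceeds 2.074 × √(2/12) = 0.85 pooled standard deviations.

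**Working it through.** The documents state no family-wise error rate, so there is no planned figure to reproduce. The only stated number, 24 participants = 2 × 12 per arm (section 5.7.6), rests on a pilot-study rule of thumb and involves no error rate.

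**Inputs from the documents**
- Per-test level 0.05, sidedness not stated (5.7.12); taken as two-sided.
- Capture formats: 2 (Antibody analysis).
- Peptide pools: 7 + 3 = 10 (Peptides).
- Participants: 12 per arm (5.7.6).
- Visits: Days 0, 30 and 120 (5.7.8). Both arms receive the same subcutaneous first dose (5.6; Arms and Interventions), and the routes differ only at the second dose on Day 90. Day 120 is therefore the only listed time point at which a route difference can exist.

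**Input not in the documents**
- Correlation between readouts: assumed, 0 to 0.9.

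**Step 1. Count.** 2 + 10 = 12 readouts at Day 120, if all are compared.

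**Step 2. Independent tests.** Chance of at least one false positive in k tests = 1 − 0.95^k.

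| Readouts tested | Calculation | Result |
|---|---|---|
| 12 (both formats, ten pools) | 1 − 0.95^12 | 46.0% |
| 11 (one format, ten pools) | 1 − 0.95^11 | 43.1% |
| 2 (one antibody, one T-cell) | 1 − 0.95^2 | 9.75% |

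If the Wilcoxon test is used in exact form, its true size at 12 versus 12 is 0.0449, and 12 independent tests give 1 − (1 − 0.0449)^12 = 42.4%.

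**Step 3. Correlated tests.** Simulation with 20,000 runs per setting, normal data, 12 per arm, 12 readouts, t-tests and no true difference. The first results column has one common correlation among all 12 readouts. The second has correlation only within the two antibody readouts and within the ten T-cell readouts.

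| Assumed correlation | Common to all 12 | Within each type only |
|---|---|---|
| 0 | 46% | 46% |
| 0.3 | 40% | 42% |
| 0.5 | 32% | 36% |
| 0.7 | 24% | 29% |
| 0.9 | 14% | 19% |

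Even at a correlation of 0.9, the rate is about three to four times the nominal 5%.

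**The case against.** The plan never says that each format and each pool will be tested between arms. Section 5.7.8 lists one ELISA and one ELISpot variable. The word *or* between the capture antibodies may mean that only one is used. The Antibody analysis text describes incubating B cell line supernatants rather than participant serum, so it is weak evidence of which antibody endpoints are planned. The Peptides text describes how pools are made, not how they are analysed, and they could be summed. On that reading there may be only two tests and a joint rate near 10%. This stands: the number of tests is undefined, and 12 is the count of readouts described. It does not settle the matter, because the plan excludes no readout and leaves the choice open until the data are seen.

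The readouts also come from the same 24 people, and four of the ten pools are NS3 from different serotypes, so positive correlation is likely. This stands too, and is why 46% is an approximate upper value.

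A reader might infer a still higher rate by multiplying the 12 readouts by two or three visits. The documents do not support that. Days 0 and 30 precede any difference in route, and both objectives are confined to the period after the second dose.

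Finally, this is a pilot sized for preliminary estimates, with objectives phrased as evaluation and no decision that depends on a P value. That lowers the weight of a formal error rate. It also argues for the fix, since a blanket significance rule over unspecified readouts fits poorly with a study meant to estimate.

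**Conclusion.** The concern holds in limited form. The plan applies an unadjusted 0.05 rule and does not identify the readout that answers either primary objective. If all 12 described readouts were compared at Day 120, the chance of at least one false route difference could reach about 46% under independence. It would be about 32% to 36% at an assumed correlation of 0.5 and 14% to 19% at 0.9. The full range for assumed correlations of 0.3 to 0.9 is roughly 14% to 42%. With only two independent readouts it is about 10%. These figures rest on an assumed number of tests and an assumed correlation; the documents give neither.

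A reader might infer that the plan misstates its error rate. It does not: 0.05 is given as a per-test threshold and no family-wise rate is claimed. The defect is an unspecified primary readout, which allows selection after the fact. It is worth correcting because the correction changes what the pilot can conclude and costs very little.

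**What to change.** Before any between-arm analysis, amend section 5.7.12 as follows.

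1. Name one antibody readout and one T-cell readout at Day 120 as primary. Examples are anti-E IgG and a pre-defined summed spot count. The sponsor should list which pools enter the sum: a dengue 2-only sum would leave out the NS3 pools of the other three serotypes.
2. State that each primary readout is tested at 0.05 because it answers a separate objective, and that the joint false-positive rate is then up to about 10%. On that basis no further adjustment is needed.
3. State that total interferon-gamma spots do not separate CD4 from CD8 responses, so a summed count does not answer that part of the second objective.
4. Report all other formats, pools and visits as exploratory, with estimates and 95% confidence intervals and no significance label.

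Section 5.7.10 links laboratory results to participant information only at the final stage, which gives a natural deadline for fixing the choice.

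The cost is wording only, with no change to visits, samples, assays or participant numbers. The downside is that single-pool results can no longer be called significant. This is a cheap improvement.
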